**Figure 4-1 Study Design**

\*Following Protocol Amendment 4, study participants are unblinded, with an opportunity for those patients still on study treatment in the placebo combination to cross-over to the LEE011 combination. Cross-over is optional and will be conducted only upon documented consent of the study patient.

An Independent Data Monitoring Committee (IDMC) will be constituted and will monitor safety and efficacy as outlined in Section 8.6 and Section 10.7. A Steering Committee (SC) will be established comprised of investigators and Novartis personnel participating in the trial to

ensure transparent management of the study according to the protocol as outlined in [Section 8.7](#).

If the study proceeds after a positive effect on PFS is declared (at final analysis of PFS), crossover to the experimental arm from the control arm is not permitted and investigators and patients will remain blinded to study treatment; all patients will continue to be followed for OS until the final OS analysis.

#### **4.1.1 Screening phase**

Men and postmenopausal women with HR+, HER2-negative advanced breast cancer will be screened for eligibility during the period up to 28 days immediately prior to starting the combination of fulvestrant + ribociclib or fulvestrant + placebo on study Day 1. During this time, the inclusion and exclusion criteria will be assessed and all screening assessments, laboratory tests, and procedures will be performed. Requested tumor tissue will be retrieved. Results of all screening/baseline evaluations must be reviewed by the investigator or his/her designee prior to patient enrollment into the study in order to assure that all inclusion and exclusion criteria have been satisfied.

[figure not shown]
All study patients must be thoroughly informed about all aspects of the study, including the study agents, visit schedule, required evaluations, and all regulatory requirements for informed consent. The signed informed consent must be obtained to participate in this study prior to the performance of any study-related activities. If the patient is unable to read, an impartial witness should be present during the entire informed consent discussion. Eligibility will be determined according to the inclusion/exclusion criteria as described in [Section 5](#). A list of procedures to be performed at the time of screening is summarized in [Table 7-1a](#). Patients must meet all eligibility criteria to be considered for enrollment in the study.

#### **4.1.2 Treatment phase**

Patient eligibility will be checked once all screening procedures are completed. An eligibility review and confirmation will be embedded to the Interactive Response Technology (IRT) system. Please refer to and comply with detailed guidelines in the IRT manual. The IRT system will confirm the inclusion of eligible patients and randomize them in a 2:1 ratio to one of the two treatment groups described in [Section 4.1](#).

Patients may continue study treatment until disease progression, occurrence of unacceptable toxicity, withdrawal of consent by the patient, patient is lost to follow-up, or the sponsor terminates the study. Patients will be followed for survival regardless of treatment discontinuation for any reason, and regardless of achieving the primary endpoint, until the planned number deaths for final OS analysis have been documented (except if consent is withdrawn or patient is lost to follow-up). An end of treatment visit will be performed when patients permanently discontinue study treatment.

All patients will have PK sampling; a subset (of approximately 150 patients) will have sparse PK collections on 3 occasions while the remainder will have a single trough PK sample on 3 occasions as detailed in [Section 7.2.3](#).

Following protocol amendment 4, study participants will be unblinded, with an opportunity for those patients still in the study in the arm of placebo + fulvestrant to transition to the treatment of ribociclib + fulvestrant.

Crossover is optional and will be conducted only upon documented consent of the study patient and protocol amendment 4 approval. A list of procedures to be performed is summarized in [Table 7-1b](#).

#### **4.1.3 Safety follow-up**

After discontinuation of study treatment, all patients will be followed for safety, AEs and patient reported outcomes which will be collected until 30 days after last study therapy administration, except in case of death, loss to follow up or withdrawal of consent. For details please refer to [Section 7.1.5](#).

#### **4.1.4 Efficacy follow-up**

Patients who discontinue treatment for reasons other than disease progression or withdrawal of consent for efficacy follow-up, will continue to be followed every 8 weeks for efficacy (i.e., tumor assessments and patient reported outcomes) during the first 18 months, then every 12 weeks until 36 months and thereafter as clinically indicated until disease progression, death, withdrawal of consent, loss to follow-up, subject/guardian decision. All scans will be acquired and analyzed for primary endpoint locally and will be sent to the CRO designated by Novartis for central imaging interpretation. If a patient starts a new anti-neoplastic treatment without withdrawing consent, the patient will continue to be followed for efficacy according to above specified protocol schedule until disease progression, death, withdrawal of consent, loss to follow-up, or subject/guardian decision. For further details please refer to [Table 7-1a](#) and [Table 7-1b](#) and [Section 7.1.6](#).

#### **4.1.5 Survival follow-up**

All patients will be followed for survival once they discontinue study treatment and tumor evaluations until the final number of OS events have been reached or the study is stopped for other reasons. Survival follow-up will be done every 12 weeks  $\pm$  1 week or earlier if a survival update is required to meet safety or regulatory needs. Survival information can be obtained by clinical visits or telephone calls ([Section 7.1.7](#)) until death, the patient is lost to follow-up, or the patient withdraws consent for survival follow-up.

## **4.2 Timing of interim analyses and design adaptations**

There is no planned efficacy interim analysis for the primary PFS endpoint. Interim analysis of the secondary endpoint of OS will be performed if PFS is statistically significant. as detailed in [Section 10.5.1](#) and [Section 10.7.2](#).

### 4.3 Definition of end of the study

The end of the study for a given patient is defined as when the patient permanently discontinues study treatment with ribociclib + fulvestrant or placebo + fulvestrant and all the end of trial procedures are completed.

If the primary endpoint, PFS, is statistically significant at the final PFS analysis, data collection will continue during survival follow-up and End of Study will be declared after the final number of OS events are reached (or earlier if OS reaches statistical significance at the interim analysis for OS) and after all patients have discontinued study therapy and completed the safety follow-up period (until 30 days after treatment discontinuation).

If the primary endpoint, PFS, is not statistically significant at the final PFS analysis then End of Study will be declared after all patients have discontinued study therapy and completed the safety follow-up period (until 30 days after treatment discontinuation).

Patients continuing to derive benefit from study treatment at the end of the study in the opinion of the investigator will be able to continue receiving trial therapy on a separate protocol. Alternatively Novartis will provide study treatment to the investigator as per local regulations.

Following with protocol amendment 4 and the statistically significant OS benefit demonstrated at the 2nd OS analysis, study participants will be unblinded with an opportunity for those patients still on study in the arm of placebo + fulvestrant to transition to arm of ribociclib + fulvestrant.

Crossover is optional and will be conducted only upon documented consent of the study patient.

The study will be closed when all study patients have either discontinued study treatment and completed the safety follow-up period, withdrawn consent, are lost to follow-up, or as soon as arrangements are made for ongoing access to study treatment for all patients still on study treatment, whichever happens first.

### 4.4 Early study termination

The study can be terminated at any time by Novartis. Should this be necessary, the patient should be seen as soon as possible and the assessments described in [Section 7](#) for a discontinued or withdrawn patient should be performed. The investigator may be informed of additional procedures to be followed in order to ensure that adequate consideration is given to the protection of the patient's interests. The investigator will be responsible for informing IRBs and/or ECs of the early termination of the trial.

Reasons for early termination:

- Unexpected, significant, or unacceptable safety risk to subjects enrolled in the study
- Decision based on recommendations from applicable board(s) after review of safety and efficacy data
- Discontinuation of study drug development

## 5 Population

### 5.1 Patient population

The study will include men and postmenopausal women with HR+, HER2-negative advanced (loco regionally recurrent not amenable to curative therapy or metastatic) breast cancer who received no or only one line of prior endocrine treatment for advanced breast cancer.

Patients with symptomatic visceral disease or any disease burden that makes the patient ineligible for endocrine therapy per the investigator's best judgment will not be included in this study.

The investigator or designee must ensure that only patients who meet all the following inclusion and none of the exclusion criteria are offered treatment in the study.

The patients are not permitted to participate in any additional parallel investigational drug or device studies.

### 5.2 Inclusion criteria

Patients eligible for inclusion in this study have to meet **all** of the following criteria:

Written informed consent must be obtained prior to any screening procedures.

1. [Retired from protocol version 0.0]

1a. Patient is an adult male/female  $\geq 18$  years old at the time of informed consent and has signed informed consent before any trial related activities and according to local guidelines.

Note: sexually active males should use a condom during intercourse while taking drug and for 21 days after stopping medication and should not father a child in this period. A condom is required to be used also by vasectomized men as well as during intercourse with a male partner in order to prevent delivery of the drug via seminal fluid.

2. Female patients must be postmenopausal. Postmenopausal status is defined either by:

- Prior surgical bilateral oophorectomy (with or without hysterectomy)
- Age  $\geq 60$
- Age  $< 60$  and amenorrheic for 12 or more months in the absence of chemotherapy, tamoxifen, toremifene, or ovarian suppression and FSH and estradiol in the postmenopausal range per local normal range

**Note:** For women with therapy-induced amenorrhea, serial measurements of FSH and/or estradiol are needed to ensure postmenopausal status ([NCCN 2.2015](#)). Ovarian radiation or treatment with a luteinizing hormone-releasing hormone agonist (LH-RHa) (goserelin acetate or leuprolide acetate) is not permitted for induction of ovarian suppression for the purpose of this trial.

3. Patient has a histologically and/or cytologically confirmed diagnosis of estrogen-receptor positive and/or progesterone receptor positive breast cancer by local laboratory (based on most recent analyzed biopsy).

4. Patient has HER2-negative breast cancer (based on most recent analyzed biopsy) defined as a negative in situ hybridization test or an IHC status of 0, 1+ or 2+. If IHC is 2+, a negative in situ hybridization (FISH, CISH, or SISH) test is required by local laboratory testing.
5. Patient must have either:
  - Measurable disease, i.e., at least one measurable lesion as per RECIST 1.1. (a lesion at a previously irradiated site may only be counted as a target lesion if there is a clear sign of progression since the irradiation).OR
  - If no measurable disease is present, then at least one predominantly lytic bone lesion must be present (patients with no measurable disease and only one predominantly lytic bone lesion that has been previously irradiated are eligible if there is documented evidence of disease progression of the bone lesion after irradiation).
6. Patient has advanced (loco regionally recurrent not amenable to curative therapy (e.g. surgery and/or radiotherapy) or metastatic) breast cancer.

Patients may be :

- newly diagnosed advanced/ metastatic breast cancer, treatment naïve
- relapsed with documented evidence of relapse more than 12 months from completion of (neo)adjuvant endocrine therapy with no treatment for advanced/metastatic disease
- relapsed with documented evidence of relapse on or within 12 months from completion of (neo)adjuvant endocrine therapy with no treatment for advanced/metastatic disease
- relapsed with documented evidence of relapse more than 12 months from completion of (neo)adjuvant endocrine therapy and then subsequently progressed with documented evidence of progression after one line of endocrine therapy (with either an antiestrogen or an aromatase inhibitor) for advanced/metastatic disease
- advanced/metastatic breast cancer at diagnosis that progressed with documented evidence of progression after one line of endocrine therapy (with either an antiestrogen or an aromatase inhibitor)

**Note:** Patient who relapsed with documented evidence of relapse on/or within 12 months from completion of (neo)adjuvant endocrine therapy and then subsequently progressed with documented evidence of progression after one line of endocrine therapy (with either an antiestrogen or an aromatase inhibitor) for metastatic/advanced disease will NOT be included in the study.

7. Patient has an Eastern Cooperative Oncology Group (ECOG) performance status 0 or 1
8. [Retired from protocol version 0.0]
  - 8a. Patient has adequate bone marrow and organ function as defined by the following laboratory values (as assessed by central laboratory for eligibility):
    - Absolute neutrophil count  $\geq 1.5 \times 10^9/L$
    - Platelets  $\geq 100 \times 10^9/L$
    - Hemoglobin  $\geq 9.0$  g/dL
    - INR  $\leq 1.5$
    - Serum creatinine  $< 1.5$  mg/dL

- Total bilirubin < ULN except for patients with Gilbert's syndrome who may only be included if the total bilirubin is  $\leq 3.0 \times \text{ULN}$  or direct bilirubin  $\leq 1.5 \times \text{ULN}$ .
- Aspartate transaminase (AST) <  $2.5 \times \text{ULN}$ , except for patients with liver metastasis, who are only included if the AST is <  $5 \times \text{ULN}$
- Alanine transaminase (ALT) <  $2.5 \times \text{ULN}$ , except for patients with liver metastasis, who are only included if the ALT is <  $5 \times \text{ULN}$
- Patient must have the following laboratory values within normal limits or corrected to within normal limits with supplements before the first dose of study medication:
  - Sodium
  - Potassium
  - Magnesium
  - Total Calcium (corrected for serum albumin)

### 5.3 Exclusion criteria

Patients eligible for this study must **not** meet **any** of the following criteria:

1. Patient with symptomatic visceral disease or any disease burden that makes the patient ineligible for endocrine therapy per the investigator's best judgment.
2. Patient has received prior treatment with chemotherapy (except for neoadjuvant/ adjuvant chemotherapy), fulvestrant or any CDK4/6 inhibitor.
3. Patients has received prior neoadjuvant/adjuvant treatment with anthracyclines at cumulative doses of  $450\text{mg}/\text{m}^2$  or more for doxorubicin or  $900\text{ mg}/\text{m}^2$  or more for epirubicin.
4. Patient with a known hypersensitivity to any of the excipients of ribociclib or fulvestrant.
5. Patient with inflammatory breast cancer at screening.
6. Patient is concurrently using other anti-cancer therapy.
7. Patient has had major surgery within 14 days prior to starting study drug or has not recovered from major side effects.
8. Patients with Child pugh score B or C.
9. Patient is currently receiving warfarin or other Coumadin derived anti-coagulant, for treatment, prophylaxis or otherwise. Therapy with heparin, low molecular weight heparin (LMWH), or fondaparinux is allowed.
10. Patient has not recovered from all toxicities related to prior anticancer therapies to NCI CTCAE version 4.03 Grade  $\leq 1$ . Exception to this criterion: patients with any grade of alopecia are allowed to enter the study.
11. Patient has received radiotherapy  $\leq 4$  weeks or limited field radiation for palliation  $\leq 2$  weeks prior to randomization, and who has not recovered to grade 1 or better from related side effects of such therapy (with the exception of alopecia) and/or from whom  $\geq 25\%$  (Ellis 1961) of the bone marrow was irradiated.
12. Patient has a concurrent malignancy or malignancy within 3 years of randomization, with the exception of adequately treated, basal or squamous cell skin carcinoma or curatively resected cervical cancer.

13. Patients with central nervous system (CNS) involvement unless they meet ALL of the following criteria:
  - At least 4 weeks from prior therapy completion (including radiation and/or surgery) to starting the study treatment.
  - Clinically stable CNS tumor at the time of screening and not receiving steroids and/or enzyme inducing anti-epileptic medications for brain metastases.
14. Patient has impairment of gastrointestinal (GI) function or GI disease that may significantly alter the absorption of the study drugs (e.g., ulcerative diseases, uncontrolled nausea, vomiting, diarrhea, malabsorption syndrome, or small bowel resection).
15. Patient has a known history of HIV infection (testing not mandatory)
16. Patient has any other concurrent severe and/or uncontrolled medical condition that would, in the investigator's judgment, cause unacceptable safety risks, contraindicate patient participation in the clinical study or compromise compliance with the protocol: (e.g. chronic pancreatitis, chronic active hepatitis, active untreated or uncontrolled fungal, bacterial or viral infections, etc.)
17. [Retired from protocol version 0.0]
- 17a. Clinically significant, uncontrolled heart disease and/or cardiac repolarization abnormality including any of the following:
  - History of angina pectoris, symptomatic pericarditis, or coronary artery bypass graft (CABG), myocardial infarction within 6 months prior to study entry
  - Documented cardiomyopathy
  - Left Ventricular Ejection Fraction (LVEF) < 50% as determined by Multiple Gated acquisition (MUGA) scan or echocardiogram (ECHO)
  - Long QT syndrome or family history of idiopathic sudden death or congenital long QT syndrome, or any of the following:
    - Risk factors for Torsades de Pointe (TdP) including uncorrected hypokalemia or hypomagnesemia, history of cardiac failure, or history of clinically significant/symptomatic bradycardia
    - Concomitant medication(s) with a known risk to prolong the QT interval and/or known to cause Torsades de Pointe that cannot be discontinued or replaced by safe alternative medication (e.g. within 5 half-lives or 7 days prior to starting study drug)
    - Inability to determine the QTcF interval
  - Clinically significant cardiac arrhythmias including but not limited to (e.g., ventricular tachycardia), complete left bundle branch block, high-grade AV block (e.g., bifascicular block, Mobitz type II and third degree AV block)
  - Systolic Blood Pressure (SBP) >160 mmHg or <90 mmHg
  - Bradycardia (heart rate < 50 bpm at rest), by ECG (mean of triplicate) and pulse.
  - Tachycardia (heart rate > 90 bpm at rest), by ECG (mean of triplicate) and pulse.
  - On screening, inability to determine the QTcF interval on the ECG (ie: unreadable or not interpretable) or QTcF >450 msec (using Fridericia's correction). All as determined by screening ECG (mean of triplicate ECGs).

18. Patient is currently receiving any of the following substances and cannot be discontinued 7 days prior to Cycle 1 Day 1:
- Known strong inducers or inhibitors of CYP3A4/5, including grapefruit, grapefruit hybrids, pummelos, star-fruit, and Seville oranges.
  - Medications that have a narrow therapeutic window and are predominantly metabolized through CYP3A4/5.
  - Herbal preparations/medications, dietary supplements (except vitamins).
19. Patient is currently receiving or has received systemic corticosteroids  $\leq 2$  weeks prior to starting study drug, or who have not fully recovered from side effects of such treatment.  
**Note:** The following uses of corticosteroids are permitted: single doses, topical applications (e.g., for rash), inhaled sprays (e.g., for obstructive airways diseases), eye drops or local injections (e.g., intra-articular).
20. Participation in a prior investigational study within 30 days prior to enrollment or within 5-half lives of the investigational product, whichever is longer.
21. Not able to understand and to comply with study instructions and requirements.

## 6 Treatment

### 6.1 Study treatment

For this study, the term “investigational drug” refers to Novartis study drug ribociclib. Fulvestrant is also being used in this study. Study treatment in this study refers to the combination of drugs in each of the study arms and includes ribociclib/placebo and fulvestrant.

Ribociclib will be supplied by Novartis or its designee as 200 mg hard gelatin capsules as individual patient supply packaged in bottles.

Fulvestrant will be procured locally according to local practice and regulation, or supplied by Novartis (or its designee). Storage conditions are described in the medication label. Medication labels will comply with the legal requirements of each country and be printed in the local language.

All dosages prescribed and dispensed to the patient and all dose changes during the study must be recorded on the Dosage Administration Record eCRF.

The study met its primary efficacy endpoint (PFS) at the time of the primary analysis. It also met the secondary efficacy endpoint of OS at the time of the pre-planned 2nd interim OS analysis.

Given the demonstrated survival benefit, patients and investigators will be unblinded to the treatment allocation. Additionally, patients who remain on study and are currently allocated to the placebo + Fulvestrant arm, will be given the opportunity to transition to the ribociclib + Fulvestrant combination.

Unblinded study treatment period will end once a patient discontinues from the study treatment for any reason or the end of study (EOS) is declared, whichever occurs first.

Following protocol amendment 4 and the unblinding of study participants, the word “placebo” refers to the original treatment allocation in the study. Physical placebo capsules no longer need to be administered but the reference to placebo has been kept in places in the protocol to avoid confusion.

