### **6.3.2 Treatment assignment or randomization**

Patients will be randomized to one of the **two** treatment arms ([Section 4.1](#) and [Section 6.1](#)) in a ratio of 2:1.

Randomization will be stratified by the following factors:

1. Lung or liver metastases: (yes versus no)
2. Previous endocrine therapy

The randomization numbers will be generated using the following procedure to ensure that treatment assignment is unbiased and concealed from patients and investigator staff. A patient randomization list will be produced by the Interactive Response Technology (IRT) provider using a validated system that automates the random assignment of patient numbers to randomization numbers. These randomization numbers are linked to the different treatment arms, which in turn are linked to medication numbers. A separate medication randomization list will be produced by or under the responsibility of Novartis Global Clinical Supply (GCS) using a validated system that automates the random assignment of medication numbers to medication packs containing each of the study treatments.

Prior to dosing, all patients who fulfill all inclusion/exclusion criteria will be randomized via IRT to one of the treatment arms. The investigator or his/her delegate will call or log on to the IRT and confirm that the patient fulfills all the inclusion/exclusion criteria. The IRT will assign a randomization number to the patient, which will be used to link the patient to a treatment arm and will specify a unique medication number for the first package of study treatment to be dispensed to the patient. The randomization number will not be communicated to the caller.

Following protocol amendment 4, patients will be unblinded to their treatment allocation.

Additionally, patients who are currently allocated to the placebo combination arm and still on study treatment, will be given the opportunity to transition to the LEE011 combination.

Those patients on the placebo arm who do not wish to cross-over from placebo to LEE011 can remain on their current treatment allocation (i.e. fulvestrant alone).

All of the study treatment cross-over registration and dispensing will be managed by the study IRT system. After transition to the investigational treatment, placebo dispensing in IRT will stop. Comparator treatment (i.e. fulvestrant) will continue to be managed locally.

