Study days			-28 to -1	-7 to -1	1	15	1	15	1	1	Within 15 days from last dose	Last dose + 30 days	Every 8 weeks (if applicable)		Every 12 weeks
Patient Quality of life questionnaires															
EORTC QLQ-C30	D	7.2.6.1	x		NA after protocol amendment 4.										
EQ-5D-5L	D	7.2.6.2	x		NA after protocol amendment 4.										
BPI-SF	D	7.2.6.3	x		NA after protocol amendment 4.										
Study Drug administration															
fulvestrant	D				x	x	x		x	x					
ribociclib (LEE011) / placebo	D				Day 1 to Day 21 daily, Day 22 to Day 28 off										
Discontinuation															
IRT – Discontinuation	S	7.1.3									x				
Antineoplastic therapies since discontinuation of study treatment	D	7.1.6									x	x	x		x
Survival follow-up	D	7.1.7													x

**Table 7-1b Visit evaluation schedule – Cross over treatment phase for patients who cross over from placebo to LEE011 after protocol amendment 4.**

Visit name	Category	Reference to Protocol Section	Treatment Phase - only applies to cross-over patients for cross over treatment cycles						Post treatment follow-up phase			Survival phase	
			Cross over Cycle 1		Cross over Cycle 2		Cross over Cycles 3 to 6	All subsequent Cross over cycles	End of study treatment (EOT)	Safety follow-up	Efficacy follow-up	End of post-treatment follow-up	Survival follow-up
Study days			1	15	1	15	1	1	Within 15 days from last dose	Last dose + 30 days	Every 8 weeks (if applicable)		Every 12 weeks
Dispensing													
IRT – cross over registration			x										
IRT – study drug administration			x		x		x	x	x				
Physical Examination													
Physical examination	S	7.2.2.1	x		x		x	Every 3 rd cycle	x				
Performance status (ECOG)	D	7.2.2.4	x		x		x	Every 3 rd cycle	x				
Weight	D	7.2.2.3	X		x		x	As clinically indicated	x				
Vital signs	D	7.2.2.2	x		x		x	Every 3 rd cycle	x				
Laboratory assessments													

Visit name	Category	Reference to Protocol Section	Treatment Phase - only applies to cross-over patients for cross over treatment cycles						Post treatment follow-up phase			Survival phase		
			Cross over Cycle 1		Cross over Cycle 2		Cross over Cycles 3 to 6	All subsequent Cross over cycles	End of study treatment (EOT)	Safety follow-up	Efficacy follow-up	End of post-treatment follow-up	Survival follow-up	
Study days			1	15	1	15	1	1	Within 15 days from last dose	Last dose + 30 days	Every 8 weeks (if applicable)		Every 12 weeks	

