2.1.8 On-treatment assessment/event

Safety summaries and selected summaries of deaths will summarize only on-treatment assessments/events.

Double-blind on-treatment period:

An on-treatment assessment/event is defined as any assessment/event in the following time interval:

[date of first administration of study treatment, the earliest between the date of last administration of study treatment + 30 days and the date of first administration of cross-over open-label ribociclib plus fulvestrant treatment – 1 day], i.e., including the lower and upper limits.

The double-blind on-treatment period is the **default** on-treatment period used in the analyses unless specified otherwise.

Cross-over on-treatment period:

An on-treatment assessment/event is defined as any assessment/event in the following time interval: [date of first administration of the cross-over open-label ribociclib plus fulvestrant treatment, date of last administration of the cross-over open-label ribociclib plus fulvestrant treatment + 30 days], i.e., including the lower and upper limits.

(Note: However, the calculation of study treatment duration will use different rules as specified in [Section 3.5.1](#)).

An AE started in the screening phase and ongoing in the on-treatment phase will not be considered as an on-treatment AE unless it has worsened.

If the last date of study treatment is missing, any assessment/event occurring after the start of study treatment will be considered as on-treatment.

Data listings will include all assessments/events, flagging those which are not on-treatment.

Note: The date of first administration of study treatment and the date of last administration of study treatment are defined in [Sections 2.1.4](#) and [2.1.5](#), respectively.

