3.5.5 Discontinuation of study treatment components

The reasons for discontinuation of ribociclib/placebo will be summarized by treatment arm for the double-blind on-treatment period, based on the information on the ribociclib/placebo DAR CRF for patients who have the “dose permanently discontinued” box checked.

Partial discontinuation: A partial discontinuation is defined as the event when the last non-zero dose of ribociclib/placebo is more than 21 days before the last non-zero dose of fulvestrant when the permanent discontinuation checkbox is checked in the ribociclib/placebo DAR page. Partial discontinuation of ribociclib/placebo will be summarized by treatment for the double-blind on-treatment period.

The reasons for discontinuation and partial discontinuation will be listed using the cross-over analysis set separately.

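### Final SAP 3.5.5 has no exclusion for placebo capsules stopped because of Amendment 4, so such stops can be counted as partial discontinuations, in the placebo column only

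*Protocol*

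**What the plan says.** Protocol 6.1, as amended, states that "Physical placebo capsules no longer need to be administered". Protocol 6.3.2 adds that "Those patients on the placebo arm who do not wish to cross-over from placebo to LEE011 can remain on their current treatment allocation", and explains that this means fulvestrant alone. For patients who do cross over, the same section says "After transition to the investigational treatment, placebo dispensing in IRT will stop"; it has no matching sentence for those who decline. Table 7-1a, the schedule for patients who continue their randomized treatment after Amendment 4, still lists ribociclib/placebo as "Day 1 to Day 21 daily, Day 22 to Day 28 off".

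The final SAP, written for Amendment 4, defines partial discontinuation in 3.5.5 by two conditions that must both hold: "the last non-zero dose of ribociclib/placebo is more than 21 days before the last non-zero dose of fulvestrant", and the permanent-discontinuation box is ticked on the ribociclib/placebo page of the dosage administration record (DAR). The count is tabulated by arm for the double-blind on-treatment period. The same section tabulates reasons for stopping ribociclib/placebo, by arm and for the same period, in every patient with the box ticked.

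Final SAP 2.1.8 ends that period at "the earliest between the date of last administration of study treatment + 30 days and the date of first administration of cross-over open-label" treatment, less one day. Final SAP 2.1.5 defines last administration of study treatment by any component, so fulvestrant alone extends it.

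**The concern.** A placebo patient who stays on fulvestrant after Amendment 4 and stops the capsules does so because the protocol no longer requires them, not because of tolerability, progression or choice. On the record this looks the same as a patient who gave up study drug and kept fulvestrant. The SAP sets out cross-over rules in detail but has no rule for the patient who declines cross-over.

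The stop can occur in one arm only, because ribociclib patients keep their capsules. Each such record coded as a permanent discontinuation adds to the placebo count and nothing to the ribociclib count. The by-arm comparison of stopping study drug while keeping fulvestrant then shows a smaller gap than true discontinuations would give, or a reversed one. Time on open fulvestrant alone is also reported under a double-blind label.

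**Working it through.** The plan gives no figure for this, so there is nothing to reproduce. There are two checks: whether the rule captures these patients, and how many there could be.

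**1. The rule applied to the calendar**

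Inputs: capsules on Days 1 to 21 of a 28-day cycle, and fulvestrant on Day 1 of each cycle after the Cycle 1 loading dose (Protocol 6.1.1 and Table 6-1); threshold of more than 21 days (final SAP 3.5.5). Gap = day of last fulvestrant dose minus day of last capsule, counting from Day 1 of the last cycle with capsules.

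| Last capsule | One later injection (Day 29) | Two later injections (Day 57) |
|---|---|---|
| Day 21 | 29 − 21 = 8, not met | 57 − 21 = 36, met |
| Day 14 | 29 − 14 = 15, not met | 57 − 14 = 43, met |
| Day 7 | 29 − 7 = 22, met | 57 − 7 = 50, met |

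After a completed 21-day course the date condition is met at the second later injection. If the capsules end by Day 7, one later injection is enough. A patient who crosses over at the next visit has the last double-blind fulvestrant dose on Day 1 and the last capsule on Day 21. The gap is 1 − 21 = −20 days, which is not met. The point therefore concerns those who decline cross-over.

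The date condition is only half of the partial-discontinuation rule; the ticked box is the other half. The reasons table needs the tick alone.

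**2. How many patients could be affected**

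The documents give no count. Inputs for an illustration:
- 727 randomized 2:1, so 727/3 ≈ 242 on placebo.
- Enrolment June 2015 to June 2016 and Amendment 4 dated 29 January 2020. Time since randomization t is taken as uniform on 43.5 to 55.5 months.
- Planning control medians in Protocol 10.8: 18 months first line (40% of patients) and 6.5 months second line (60%).
- Assumption: exponential progression-free time stands in for still being on treatment.

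Proportion still on treatment = mean over t of 0.4·exp(−ln2·t/m1) + 0.6·exp(−ln2·t/m2), where m1 and m2 are the first- and second-line medians.

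- Planning medians 18/6.5: 0.0600 + 0.0033 = 0.0633; × 242.3 = 15.3 patients.
- Low end of the ranges cited in Protocol 10.8, 8/4.8: 0.0057 + 0.0005 = 0.0063; × 242.3 = 1.5 patients.
- High end, 23/6.5: 0.0905 + 0.0033 = 0.0938; × 242.3 = 22.7 patients.

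These are patients still on treatment, so they are ceilings. With the planning medians, the number declining cross-over is 1.5 if 10% decline (0.6% of the arm), 7.7 if 50% decline (3.2%) and 15.3 if all decline (6.3%).

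**The case against.** The strongest objection is that the SAP does not count every placebo stop. It also requires the permanent-discontinuation box, and the documents do not say how sites code capsules that lapse under Amendment 4. If the box is left blank, the count is zero. This stands, and it makes the effect conditional. It does not remove the point, because for any patient coded as a permanent stop the rule as written counts the stop, and uneven coding across sites would make the table inconsistent.

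The protocol wording is also permissive, and Table 7-1a still shows daily ribociclib/placebo for continuing patients. Protocol 6.1 explains that references to placebo were retained and now denote the original allocation, which probably accounts for the table. The three places still need to be reconciled.

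A reader might infer that ribociclib will look better tolerated overall than it was. The documents do not support that. Protocol 10.5.3.5 studies tolerability through dose reductions and interruptions due to adverse events, and final SAP 3.7.1.4 tabulates adverse events leading to discontinuation, reduction and interruption. An amendment-driven stop enters none of these. It is not an adverse event, and an interruption requires a resumed dose (3.5.4). Relative dose intensity for placebo is computed over a duration that ends at the last capsule. The ribociclib arm's own rate does not change, and a recorded administrative reason would be visible in the reasons table. The SAP for the primary analysis defines the same partial-discontinuation summary, and that analysis came about two years before Amendment 4.

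A reader might also want to express the excess as a multiple of the true placebo rate. No such rate is given, so no multiple can be supported. Nor can one assume that every remaining placebo patient declines cross-over once a survival benefit has been shown.

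**Conclusion.** The gap is real and minor. Final SAP 3.5.5 does not separate placebo stops caused by Amendment 4 from other stops, and the double-blind window in 2.1.8 runs on past unblinding for patients who decline cross-over. Where the box is ticked, the rule adds stops unrelated to tolerability to the placebo column of two descriptive tables, and the bias can only favour ribociclib.

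The size cannot be fixed from the documents. Under the planning medians about 15 of 242 placebo patients (6.3%) might still be on treatment, with about 1.5 to 23 across the cited ranges. Those affected are the subset who decline cross-over, are coded as permanently discontinued and, for the partial-discontinuation count, usually receive two more injections. The estimate treats progression-free status as time on treatment, which overstates it, since patients also stop for other reasons. PFS, OS and type I error control are untouched.

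**What to change.** In final SAP 3.5.5, exclude from both the partial-discontinuation count and the discontinuation totals any placebo stop made because of Amendment 4 or unblinding. Identify it from the reason on the DAR page or, where that is unclear, from a last placebo dose that coincides with the patient's transition to Amendment 4. Show these patients in a separate row, such as *placebo capsules stopped due to Amendment 4*, and keep them in the denominator. Placebo stops made earlier for other reasons continue to count as now.

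The rule should not depend on an individual unblinding date. The SAP names a cross-over date, which decliners do not have, and the documents do not show that an unblinding date is recorded for them. Protocol 6.1, 6.3.2 and Table 7-1a should also be reconciled on what continuing placebo patients receive.

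The cost is a sentence or two in the SAP and a small amount of programming and data review to flag the records.
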